11.2 Low Luminance Visual Acuity (LLVA)

For each cohort, change from baseline in LLVA total letters read at the treatment completion visit and post-treatment follow-up visit will be assessed using Student's paired t-test similar to the analysis of primary outcome as outlined in Section 9.1 for the study eye. Additionally, a model similar to Model 1 will be fitted to assess the mean difference in total letters read in the study eye

at the treatment completion visit and post-treatment follow-up visit compared to baseline in Cohort 1 (Table 10).

11.3 Low Luminance Questionnaire (LLQ)

For each cohort, change from baseline at the treatment completion visit and post-treatment follow-up visit for each subscale and the composite score will be assessed using Student's paired t-test similar to the analysis of the primary outcome as outlined in Section 9.1. Additionally, a model similar to Model 1 will be fitted to assess the mean difference in the composite score at the treatment completion visit and post-treatment follow-up visit compared to baseline in Cohort 1 (Table 11).

12.0 SAFETY OUTCOMES

These presentations will be based on the safety population. All relevant information will be listed.

12.1 Adverse Events (AEs)

AEs reported throughout the study period will be presented in a listing with details including date reported, description, severity, relatedness to IP, outcome and date resolved. Total number and percentage of participants with AEs will be summarized by cohort and overall and categorized by severity of the AE, ocular specification (ocular vs. systemic), outcome, and relation to IP (Table 12).

AEs will also be summarized by system organ class (SOC) and preferred term (PT) (Table 13). If sufficient data are present, summaries similar to Table 12 and Table 13 will be generated for all serious adverse events (SAEs).

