4.0 STUDY DESIGN AND METHODS

This is a prospective, uncontrolled, single center, pilot study to investigate the potential efficacy and safety of taking 16,000 IU (Cohort 1) or 48,000 IU (Cohort 2) of vitamin A palmitate in improving dark adaptation in participants with AMD and abnormal dark adaptation.

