4.3 Study Design and Procedures

The study duration will be three months for the first cohort during which participants will be instructed to take vitamin A palmitate 16,000 IU daily by mouth for two months. In the second cohort, the study duration will be two months and the participants will be instructed to take vitamin A palmitate 48,000 IU daily by mouth for one month. In addition, there will be a screening visit between 60 days and one day prior to the baseline visit. For the first cohort, the primary outcome will be assessed at baseline versus Month 2 and the secondary outcomes will be assessed at baseline versus Month 2 and baseline versus Month 3. For the second cohort, the primary outcomes will be assessed at baseline versus Month 1 and the secondary outcomes will be assessed at baseline versus Month 1 and baseline versus Month 2. For both cohorts, visits will occur at baseline, and then monthly and as clinically indicated. The study will require five visits for the first cohort and four visits for the second cohort. All visits must be conducted within a window of \pm 14 days from the target day. At each visit, the participant will undergo a review of systems, such as an assessment of headache frequency and severity, as well as an assessment of safety variables. The tests scheduled at each visit may be split and completed within seven days (including the 7th day) from the visit date. A complete ophthalmologic examination will be performed at each visit to measure outcome variables. Participants will be screened with serum for hepatitis or hepatic dysfunction. However, for caution, we will monitor liver function tests. If participants in either cohort cannot tolerate the prescribed dose of vitamin A palmitate, they will be instructed to stop taking the supplement and they will be removed from the study.

If participants are on Coumadin® (Warfarin) at enrollment, they must visit their prescribing physician to check their Coumadin® status within two to four weeks after initiating IP to have their

Coumadin® regimen adjusted if necessary (as taking vitamin A and Coumadin® can increase the chances of bruising and bleeding.)

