⁶ For participants of childbearing potential only, participants must have a negative pregnancy test within 24 hours prior to dispensation of study supplement. Pregnancy tests will only be conducted at each visit if the participant is determined to be of childbearing potential. See Appendix 1 for guidance on determining whether a participant is considered to be of childbearing potential.

⁷ The tests scheduled at each visit may be split and completed within seven days (including the 7th day) from the visit date.

⁸ The study visit, treatment, and assessments at Month 3 are to be completed for Cohort 1 only.

⁹ This assessment will be completed for any participants who return the study supplement at Month 2.

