3.0 GENERAL REVIEW OF STUDY DESIGN

3.1 Study Design

The DA VitA AMD study is a prospective, uncontrolled, single center, pilot study to investigate the potential efficacy and safety of vitamin A palmitate dosing in improving dark adaptation in participants with AMD (without RPD) and abnormal dark adaptation.

The study will require five visits (screening, baseline, Month 1, Month 2, and Month 3) for Cohort 1 and four visits (screening, baseline, Month 1, and Month 2) for Cohort 2. Participants in Cohort 1 will be instructed to take vitamin A palmitate 16,000 IU daily by mouth for two months from baseline through Month 2 and will continue in the study through Month 3. Participants in Cohort 2 will be instructed to take 48,000 IU of vitamin A palmitate daily by mouth from baseline through Month 1 and will continue in the study through Month 2. The screening visit must occur between 60 days and one day prior to the baseline visit while Months 1, 2 and 3 visits must be conducted within a window of \pm 14 days from the target day. The tests scheduled at each visit may be split and completed within seven days (including the 7th day) from the visit date. At each visit, the participant will undergo a review of systems, such as an assessment of headache frequency and

severity, as well as an assessment of safety variables. A complete ophthalmologic examination will be performed at each visit to measure outcome variables. If participants in either cohort cannot tolerate the prescribed dose of vitamin A palmitate, they will be instructed to stop taking the supplement and they will be removed from the study.

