^a MedDRA version XX.X.^b System organ classes (SOCs) are presented in descending order of number of events reported; preferred terms (PTs) within each SOC are also presented in descending order of number of events reported.^c Column header counts and denominators are the number of participants in the safety population in the respective cohort or overall. Percentages are rounded to the nearest whole number. Participants are counted at most once in each row. Therefore, a participant may experience events corresponding to multiple PTs within an SOC, but the sum of participants in the PT rows may not add up to the corresponding SOC row.

Table 14. Summary of Laboratory Assessments Over Time

Visit	Abnormal Findings ^a n/N (%)		Any Change from Baseline n/N (%)		Clinically Significant Change from Baseline n/N (%)	
	Cohort 1	Cohort 2	Overall	Cohort 1	Cohort 2	Overall
Baseline	x/x (x)	x/x (x)	x/x (x)			
Month 1			x/x (x)	x/x (x)	x/x (x)	x/x (x)
Month 2			x/x (x)	x/x (x)	x/x (x)	x/x (x)
Month 3 ^b			x/x (x)	x/x (x)	x/x (x)	x/x (x)

Denominators are the number of participants in the safety population who completed the specified visit, in the respective cohort or overall. Percentages are rounded to the nearest whole number.

^a Abnormal results from screening are reported at baseline.

^b Only participants in Cohort 1 complete Month 3.

Table 15. Summary of Dark Adaptation Rod Intercept Time

Visit	Rod Intercept Time (minutes)			Change from Baseline		
	Cohort 1	Cohort 2	Overall	Cohort 1	Cohort 2	Overall
Baseline						
N	X	X	X			
Mean (SD)	x.xx (x.xxx)	x.xx (x.xxx)	x.xx (x.xxx)			
Median	x.xx	x.xx	x.xx			
Range (min, max)	(x.x, x.x)	(x.x, x.x)	(x.x, x.x)			
Month 1						
N	X	X	X	X	X	X
Mean (SD)	x.xx (x.xxx)	x.xx (x.xxx)	x.xx (x.xxx)	x.xx (x.xxx)	x.xx (x.xxx)	x.xx (x.xxx)
Median	x.xx	x.xx	x.xx	x.xx	x.xx	x.xx
Range (min, max)	(x.x, x.x)	(x.x, x.x)	(x.x, x.x)	(x.x, x.x)	(x.x, x.x)	(x.x, x.x)
Month 2						
N	X	X	X	X	X	X
Mean (SD)	x.xx (x.xxx)	x.xx (x.xxx)	x.xx (x.xxx)	x.xx (x.xxx)	x.xx (x.xxx)	x.xx (x.xxx)
Median	x.xx	x.xx	x.xx	x.xx	x.xx	x.xx
Range (min, max)	(x.x, x.x)	(x.x, x.x)	(x.x, x.x)	(x.x, x.x)	(x.x, x.x)	(x.x, x.x)
Month 3^a						
N	X			X		
Mean (SD)	x.xx (x.xxx)			x.xx (x.xxx)		
Median	x.xx			x.xx		
Range (min, max)	(x.x, x.x)			(x.x, x.x)		

^a Only participants in Cohort 1 complete Month 3.

Table 16. Summary of BCVA Total Letters Read

Visit	BCVA Total Letters Read										Change from Baseline						

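### Tables 12 and 13 show adverse events by dose cohort with participant denominators and no allowance for three months of follow-up in Cohort 1 against two in Cohort 2

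*SAP*

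**What the plan says.** On follow-up, Protocol 4.3 states: "The study duration will be three months for the first cohort", with two months of supplement, and "In the second cohort, the study duration will be two months", with one month of supplement. SAP 3.1 agrees: Cohort 2 participants are to "take 48,000 IU of vitamin A palmitate daily by mouth from baseline through Month 1 and will continue in the study through Month 2". A footnote to the flowsheet (Protocol Appendix 2) adds: "The study visit, treatment, and assessments at Month 3 are to be completed for Cohort 1 only". AE assessment is scheduled at Months 1, 2 and 3, so Cohort 1 has three scheduled AE assessments and Cohort 2 has two.

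On AE reporting, SAP 12.1 takes all AEs reported while participants are on study and states: "Total number and percentage of participants with AEs will be summarized by cohort and overall and categorized by severity of the AE". Tables 12 and 13 place Cohort 1, Cohort 2 and Overall in adjacent columns and give both participants affected and number of events. The footnote to Table 12 reads: "Column header counts and denominators are the number of participants in the safety population in the respective cohort or overall". The AE listing in SAP 12.1 carries the date reported and the date resolved. It names neither an onset date nor whether the participant was on supplement at the time.

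SAP 12.1 and 13.1 foresee similar tables for serious AEs and for natural progression of the disease, if the data suffice.

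Neither document provides a person-time denominator, an AE rate, a common observation window, a split by supplement phase or an AE table by visit. Tables 14 to 21 are laid out by visit and mark Month 3 as Cohort 1 only. Tables 12 and 13 carry no such note.

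**The concern.** Dose and duration differ together. The cohort with three times the daily dose has AEs collected for a shorter time, and a percentage of participants with at least one AE grows with the time over which AEs are collected. Two columns with the same denominator rule but different windows cannot be read side by side at face value, and the direction of the distortion in the percentages favours the higher dose.

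Safety is part of the stated aim. Protocol 4.0 frames it by dose, as the "potential efficacy and safety of taking 16,000 IU (Cohort 1) or 48,000 IU (Cohort 2) of vitamin A palmitate". Tolerability in Cohort 1 is also part of the protocol's stated background for opening Cohort 2. Tables 12 and 13 are the main display of AEs by dose, and with no formal test planned a reader will rely on them directly. The Overall column has a related problem: it averages a three-month and a two-month risk and estimates neither.

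**Working it through.** The plan states no AE rate, so there is no figure of its own to reproduce. The check asks what Tables 12 and 13 would show if the two cohorts had the same underlying rate.

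**Inputs**
- Follow-up: 3 months (target day 90) v 2 months (target day 60), from Protocol 4.3 and Appendix 2.
- Time on supplement: 2 months v 1 month, from Protocol 4.3 and SAP 3.1.
- Participants: 5 per cohort, the number SAP 5.1 aims to analyse.
- AE rate λ per person-month: **assumed**, constant and equal in both cohorts, shown from 0.05 to 1.0.

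**Step 1: ratio of observation time.** Follow-up: 90/60 = 1.5. On supplement: 60/30 = 2.0. With the ±14-day visit window, Cohort 1's last visit falls on days 76 to 104 and Cohort 2's on days 46 to 74. By visit date, Cohort 1 is followed longer even at the closest extremes (76 v 74).

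**Step 2: expected share with at least one AE**, 1 − exp(−λT), with T = 3 or 2.

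| λ per month | Cohort 1 | Cohort 2 | Gap (points) |
|---|---|---|---|
| 0.05 | 13.9% | 9.5% | 4.4 |
| 0.1 | 25.9% | 18.1% | 7.8 |
| 0.2 | 45.1% | 33.0% | 12.2 |
| 0.3 | 59.3% | 45.1% | 14.2 |
| 0.5 | 77.7% | 63.2% | 14.5 |
| 1.0 | 95.0% | 86.5% | 8.6 |

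If only on-supplement events are counted (T = 2 or 1), λ = 0.2 gives 33.0% v 18.1%.

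**Step 3: rate ratio at which the columns look equal.** Setting 1 − exp(−3λ₁) = 1 − exp(−2λ₂) gives λ₂/λ₁ = 3/2 = 1.5. For on-supplement events it is 2/1 = 2.0.

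**Step 4: Overall column.** At λ = 0.1 with five per cohort, the pooled expectation is (25.9 + 18.1)/2 = 22.0%, which is neither the two-month nor the three-month risk.

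**Step 5: chance beside the bias.** One participant in five is 20 points, more than any gap in the table. With five per cohort at λ = 0.2, binomial counts give Cohort 2 fewer affected participants with probability 0.53, a tie with 0.23 and more with 0.23.

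**Step 6: event counts.** With 5 v 5 and full follow-up at λ = 0.2, expected events are 5 × 0.2 × 3 = 3.0 v 5 × 0.2 × 2 = 2.0. This 1.5 ratio depends on cohort size and withdrawal. Cohort 2 may take up to five extra participants to cover withdrawals before one month of supplement. If those withdrawals each contribute under one month, Cohort 2 has between 5 × 2 = 10 and just under 10 + 5 = 15 person-months, against 5 × 3 = 15 in Cohort 1. The event ratio then lies between 1.5 and about 1.

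**Step 7: with person-time denominators.** At λ = 0.2: 3.0/15 = 0.20 and 2.0/10 = 0.20 per person-month. The artefact disappears.

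**The case against.** The strongest reply is that no comparison between doses is planned. SAP 5.0 calls all analyses exploratory, SAP 5.1 says the pilot will not settle safety or efficacy, and the outcome tests run within each cohort. That stands: no p-value and no stated decision rule depends on Tables 12 or 13. It does not remove the problem, because in a study without such a test the descriptive table is what readers have.

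Second, the effects the protocol anticipates are partly covered. Hepatic and other laboratory results (Table 14) and headache and papilledema (Table 20) are shown by visit and cohort, and at Month 1 both cohorts have had about 30 days of supplement. That stands for those items. Other AEs have no such display.

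Third, every AE is listed, so with about ten participants a reader could place events in time. This stands in part. The listing names the report date, and a later reconstruction would be unplanned.

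Fourth, the percentage affected over a full regimen is a legitimate descriptive quantity. It is, provided the table says that the regimens and windows differ. Tables 12 and 13 do not.

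Fifth, person-time would not make this a clean dose contrast: the cohorts are sequential and uncontrolled, and Cohort 1 participants may enter Cohort 2. That also stands, and limits what the fix can claim.

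A reader might infer that the tripled dose will look safer, or that the tables would hide a true excess of harm. The documents do not support either. The lean is in expectation only, step 5 shows that in nearly half of cases Cohort 2 would tie or show more affected participants, and nothing in the plan says what the true rates are. Nor can a fixed 1.5-fold excess of events in Cohort 1 be inferred, since that needs equal cohort sizes and full follow-up.

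**Conclusion.** The point holds as a reporting bias in a descriptive table. At equal monthly rates, the percentage of participants with an AE in Tables 12 and 13 is expected to be about 4 to 15 points lower in the higher-dose cohort over the assumed range, and a monthly rate 1.5 times higher in Cohort 2 would give equal expected percentages. The durations and denominators come from the documents. The rates, their constancy over time and full follow-up are assumptions.

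The size is modest beside chance at about five per cohort. The direction for percentages at equal rates follows from the design under those assumptions, whereas event counts also depend on cohort size and early withdrawal. It is worth correcting because the direction is known and the correction is small.

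**What to change.** In SAP 12.1 and Tables 12 and 13, and in any similar tables for serious AEs or disease progression:

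1. Keep the planned counts and percentages.
2. Add actual person-months of observation and AEs per person-month for each cohort, computed from each participant's own dates so that early withdrawal is reflected. Give the person-months behind any Overall rate.
3. Footnote that planned follow-up is 3 v 2 months, of which 2 v 1 months are on supplement.
4. If AE onset dates are captured, show on-supplement and post-supplement events separately and add the phase to the AE listing. If they are not, classify by report date and say so, noting that an event reported late may fall in the wrong phase.
5. State that any reading across doses is descriptive and imprecise.

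Items 1, 3 and 5 need only SAP and shell wording. Item 2 needs a small amount of programming from visit dates. For item 4 the sponsor must first confirm whether onset is recorded, since SAP 12.1 names only the report and resolution dates. SAP 8.1.1 also takes the dispensing visit as the date of first intake, so the start of the on-supplement phase would be approximate. Study conduct does not change. The downside is that rates on about five participants per cohort are imprecise, so they should always appear beside the counts.

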13.0 OTHER SAFETY OUTCOMES

These presentations will be based on the safety population. All relevant information will be listed.

13.1 Natural Progressions of the Disease

Events corresponding to natural progression of the disease will be listed by participant. If sufficient data are present, summaries similar to Tables 12 and 13 will be presented for these events.

13.2 Laboratory Assessments

Hepatitis screening is performed at the screening visit. Serum vitamin A levels and hepatic panels are performed at the screening visit and all follow-up visits. Abnormal results from laboratory assessments performed at screening are reported at the baseline visit.

Frequency and percentage of participants reporting laboratory abnormalities at baseline and shift from baseline at each follow-up visit will be summarized by cohort and overall as in Table 14.

14.0 OTHER OPHTHALMIC ASSESSMENTS

These presentations will be based on the safety population. All relevant information will be listed. Outcome measurements or relative change in outcome measurements may be plotted against time.

14.1 Rod-Intercept Time (RIT)

RIT, as measured by the AdaptDxTM, is assessed at baseline and all follow-up visits in the study eye. RIT at all visits and change from baseline at all follow-up visits will be presented by participant and summarized by cohort and overall as in Table 15.

14.2 Best-Corrected Visual Acuity (BCVA)

Visual acuity is assessed at baseline and all follow-up visits in both eyes. BCVA with manifest refraction is scheduled to be performed at baseline and Month 2 and if a change in BCVA total letters read of ≥ 10 (≥ 0.20 logMAR) since previous visit is observed. Values from assessments performed with manifest refraction will be used for the analysis if available; otherwise, values from assessments performed without manifest refraction will be used.

Total letters read at each visit and change from baseline at each follow-up visit will be presented by participant for both eyes and summarized by cohort and overall as in Table 16. Participants experiencing loss of ≥ 15 letters from baseline may be withdrawn from the study at investigator's discretion. Frequency and percentage of participants presenting with a loss of ≥ 15 letters from baseline at each follow-up visit will be included in Table 16.

14.3 Low Luminance Visual Acuity (LLVA)

LLVA total letters read is assessed at baseline and all follow-up visits in both eyes. Total letters read at each visit and change from baseline at each follow-up visit will be presented by participant and summarized by cohort and overall as in Table 17.

14.4 Low Luminance Questionnaire (LLQ)

The low luminance questionnaire is completed at baseline and all follow-up visits. Subscale and composite scores at baseline and change from baseline at each follow-up visit will be presented by participant and summarized by cohort and overall (Table 18).

14.5 Intraocular Pressure (IOP)

IOP is assessed at baseline and all follow-up visits in both eyes. IOP measurements at each visit and change from baseline at each follow-up visit will be presented by participant and summarized for each eye by cohort and overall as in Table 19.

14.6 Optic Nerve Papilledema, Headache, and Medication Assessment

Participants are assessed at each visit for headache and presence of optic nerve papilledema. Additionally, vitamin A palmitate consumption outside of the study is assessed at each follow-up visit. Number and percentage of participants experiencing optic nerve papilledema in each eye, headache classified by severity, and vitamin A palmitate consumption outside of the study will be summarized by cohort and overall as in Table 20; relevant information will be listed by participant.

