4.4.3 Concomitant Therapy

Participants in both cohorts may continue to receive all medications and standard treatments administered for their conditions at the discretion of their treating physician, except for high-dose vitamin A palmitate supplementation ($\geq 8,000$ IU per day). A participant will be withdrawn from the study if placed on a daily dose of $\geq 8,000$ IU of vitamin A palmitate.

There are no pharmacologic interactions known to occur between vitamin A palmitate and tetracyclines, but there is the potential for additive side effects as each drug has the potential to cause intracranial hypertension. One case report in a patient receiving high doses of vitamin A palmitate combined with minocycline reported the development of benign intracranial hypertension.²⁴ For this reason, regular ophthalmic examinations during study visits is the

recommended care for participants receiving the drug combination. Specific questions regarding headaches and attention to optic nerve for presence of papilledema will be noted at each visit.

If participants are on Coumadin® at enrollment, they must visit their prescribing physician to check their Coumadin® status within 2-4 weeks after initiating study supplementation to have their Coumadin® regimen adjusted if necessary (as taking vitamin A palmitate and Coumadin® can increase the chances of bruising and bleeding.)

All participants are eligible to receive standard-of-care treatment for AMD while enrolled in this study. However, if a participant develops neovascular AMD in the study eye during the course of the study, the participant may receive standard-of-care treatment for neovascular AMD according to the recommendations of the participant's treating retina specialist. The participant will be withdrawn from this study and the last observation will be carried forward for data analyses.

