5.3 Study Supplement-Related

While long-term vitamin A supplementation has been associated with hip fractures, short term vitamin A supplementation appears to have no effect on bone turnover.^{18, 19, 25}

Vitamin A and other retinoids as well as beta carotene, a carotenoid, have been candidate therapies in several chemoprevention studies for tobacco-related cancers. Several clinical trials have now demonstrated a surprising increase in cancer risk in participants taking beta carotene supplements.^{20,21} Vitamin A supplementation has not been associated with a higher risk of lung cancer in tobacco based trials, and additional prevention trials are ongoing.

A study of pharmacokinetic metabolites over 20 days in adult men who received vitamin A at doses equivalent to 50,000 IU found these doses consumed over this length of time did not lead to hypervitaminosis A.²⁹ Similar doses of 50,000 IU vitamin A have been explored previously in a similar population of patients with AMD with no significant side effects.¹⁷

High doses of vitamin A supplementation has also been administered in accordance with the World Health Organization (WHO) guidelines to decrease childhood mortality.³⁰ Some countries, such as South Africa, implemented a “routine periodic high -dose Vitamin A supplementation” program which provided six monthly high dose (100,000 IU to 200, 000 IU) vitamin A retinyl palmitate capsules to children without significant side effects.³⁰

There are small risks associated with chronic high-dose vitamin A toxicity.²⁸ The effects of toxicity may include hepatomegaly, elevated blood lipid levels, bone changes, and increased intracranial pressure.²⁸

A study investigating high dose vitamin A in molar pregnancy used 200,000 IU vitamin A in adult women for up to 60 days and found no significant toxic effects.³¹ Other studies show there may be a possible risk of teratogenicity in a fetus when a participant of childbearing potential consumes high doses (i.e., > 10,000 IU/day) of preformed vitamin A palmitate.²⁷ There have been reports of malformations in children when their mothers consumed high doses (>25,000 IU/day) of preformed vitamin A during pregnancy.²⁷

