Mean (SD)	x.xx (x.xxxx)	x.xx (x.xxxx)	x.xx (x.xxxx)	x.xx (x.xxxx)	x.xx (x.xxxx)	x.xx (x.xxxx)
Median	x.xx	x.xx	x.xx	x.xx	x.xx	x.xx
Range (min, max)	(x.x, x.x)	(x.x, x.x)	(x.x, x.x)	(x.x, x.x)	(x.x, x.x)	(x.x, x.x)
...						
Composite Score^b						
...						

^aOnly participants in Cohort 1 complete Month 3.^bComposite score is an average of the six weighted subscale scores.

Table 19. Summary of IOP

Visit	Baseline	IOP (mmHg)						Change from Baseline			
		Cohort 1		Cohort 2		Overall		Cohort 1		Cohort 2	
		Study Eye	Fellow Eye	Study Eye	Fellow Eye	Study Eye	Fellow Eye	Study Eye	Fellow Eye	Study Eye	Fellow Eye
	N	x	x	x	x	x	x	x	x	x	x
	Mean (SD)	x.x (x.xx)	x.x (x.xx)	x.x (x.xx)	x.x (x.xx)						
	Median	x.x	x.x	x.x	x.x						
	Range (min, max)	(x, x)	(x, x)	(x, x)	(x, x)						
Month 1	N	x	x	x	x	x	x	x	x	x	x
	Mean (SD)	x.x (x.xx)	x.x (x.xx)	x.x (x.xx)	x.x (x.xx)						
	Median	x.x	x.x	x.x	x.x						
	Range (min, max)	(x, x)	(x, x)	(x, x)	(x, x)						
Month 2	N	x	x	x	x	x	x	x	x	x	x
	Mean (SD)	x.x (x.xx)	x.x (x.xx)	x.x (x.xx)	x.x (x.xx)						
	Median	x.x	x.x	x.x	x.x						
	Range (min, max)	(x, x)	(x, x)	(x, x)	(x, x)						
Month 3^a	N	x	x	x	x	x	x	x	x	x	x
	Mean (SD)	x.x (x.xx)	x.x (x.xx)	x.x (x.xx)	x.x (x.xx)						
	Median	x.x	x.x	x.x	x.x						
	Range (min, max)	(x, x)	(x, x)	(x, x)	(x, x)						

^aOnly participants in Cohort 1 complete Month 3.

Table 20. Summary of Optic Nerve Papilledema, Headache, and Medication Assessment

Visit / Assessment	Participants with Event N (%) ^a		
	Cohort 1	Cohort 2	Overall
Baseline			
Optic Nerve Papilledema			
Study Eye			
Yes	x (x)	x (x)	x (x)
No	x (x)	x (x)	x (x)
Fellow Eye			
Yes	x (x)	x (x)	x (x)
No	x (x)	x (x)	x (x)
Headache			
None	x (x)	x (x)	x (x)
Mild	x (x)	x (x)	x (x)
Moderate	x (x)	x (x)	x (x)
Severe	x (x)	x (x)	x (x)
Month 1			
Optic Nerve Papilledema			
Study Eye			
Yes	x (x)	x (x)	x (x)
No	x (x)	x (x)	x (x)
Fellow Eye			
Yes	x (x)	x (x)	x (x)
No	x (x)	x (x)	x (x)
Headache			
None	x (x)	x (x)	x (x)
Mild	x (x)	x (x)	x (x)
Moderate	x (x)	x (x)	x (x)
Severe	x (x)	x (x)	x (x)
Vitamin A Palmitate			
Consumption Outside of Study			
Yes	x (x)	x (x)	x (x)
No	x (x)	x (x)	x (x)
Month 2			
Month 3^b			
Optic Nerve Papilledema			
Study Eye			
Yes	x (x)		
No	x (x)		
Fellow Eye			
Yes	x (x)		
No	x (x)		
Headache			
None	x (x)		
Mild	x (x)		
Moderate	x (x)		
Severe	x (x)		
Vitamin A Palmitate			
Consumption Outside of Study			
Yes	x (x)		
No	x (x)		

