^aDenominators are the number of participants in the safety population with a non-missing value for the parameter at the specified visit, in the respective cohort or overall. Percentages are rounded to the nearest whole number.

^bOnly participants in Cohort 1 complete Month 3.

Table 21. Summary of Additional Ophthalmic Assessments

Visit / Assessment	Participants with Events					
	Cohort 1		Cohort 2		Overall	
	Study Eye	Fellow Eye	Study Eye	Fellow Eye	Study Eye	Fellow Eye
Baseline						
Drusen						
No	x (x)	x (x)	x (x)	x (x)	x (x)	x (x)
Yes - small	x (x)	x (x)	x (x)	x (x)	x (x)	x (x)
Yes - intermediate	x (x)	x (x)	x (x)	x (x)	x (x)	x (x)
Yes - large	x (x)	x (x)	x (x)	x (x)	x (x)	x (x)
Hypo/hyper pigmentation						
No	x (x)	x (x)	x (x)	x (x)	x (x)	x (x)
Yes	x (x)	x (x)	x (x)	x (x)	x (x)	x (x)
RPE detachment						
No	x (x)	x (x)	x (x)	x (x)	x (x)	x (x)
Yes - drusenoid	x (x)	x (x)	x (x)	x (x)	x (x)	x (x)
Yes - non-drusenoid	x (x)	x (x)	x (x)	x (x)	x (x)	x (x)
CNV						
No	x (x)	x (x)	x (x)	x (x)	x (x)	x (x)
Yes	x (x)	x (x)	x (x)	x (x)	x (x)	x (x)
Subretinal/Intraretinal fluid						
No	x (x)	x (x)	x (x)	x (x)	x (x)	x (x)
Yes	x (x)	x (x)	x (x)	x (x)	x (x)	x (x)
Geographic Atrophy						
No	x (x)	x (x)	x (x)	x (x)	x (x)	x (x)
Yes - foveal	x (x)	x (x)	x (x)	x (x)	x (x)	x (x)
Yes - extra-foveal	x (x)	x (x)	x (x)	x (x)	x (x)	x (x)
Aphakia						
No	x (x)	x (x)	x (x)	x (x)	x (x)	x (x)
Yes	x (x)	x (x)	x (x)	x (x)	x (x)	x (x)
Pseudophakic lens						
No	x (x)	x (x)	x (x)	x (x)	x (x)	x (x)
Yes	x (x)	x (x)	x (x)	x (x)	x (x)	x (x)
Nuclear Cataract Score						
Not assessed ^b	x (x)	x (x)	x (x)	x (x)	x (x)	x (x)
Clear	x (x)	x (x)	x (x)	x (x)	x (x)	x (x)
< STD2	x (x)	x (x)	x (x)	x (x)	x (x)	x (x)
≥ STD2 but < STD3	x (x)	x (x)	x (x)	x (x)	x (x)	x (x)
≥ STD3	x (x)	x (x)	x (x)	x (x)	x (x)	x (x)
Cannot Evaluate	x (x)	x (x)	x (x)	x (x)	x (x)	x (x)
Not Done	x (x)	x (x)	x (x)	x (x)	x (x)	x (x)
PSC Cataract Score						
Not assessed ^b	x (x)	x (x)	x (x)	x (x)	x (x)	x (x)
Clear	x (x)	x (x)	x (x)	x (x)	x (x)	x (x)
< STD2	x (x)	x (x)	x (x)	x (x)	x (x)	x (x)
≥ STD2 but < STD3	x (x)	x (x)	x (x)	x (x)	x (x)	x (x)
≥ STD3	x (x)	x (x)	x (x)	x (x)	x (x)	x (x)
Cannot Evaluate	x (x)	x (x)	x (x)	x (x)	x (x)	x (x)
Not Done	x (x)	x (x)	x (x)	x (x)	x (x)	x (x)

^a Denominators are the number of participants in the safety population with a non-missing value for the parameter at the specified visit, in the respective cohort or overall. Percentages are rounded to the nearest whole number.

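### SAP 14.6 and Table 20 count headache by severity at each visit without pairing it to the participant's own baseline, and leave out frequency

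*SAP*

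**What the plan says.** Protocol 4.3 includes in the review of systems at each visit items "such as an assessment of headache frequency and severity", and SAP 3.1 repeats this. Appendix 2 of the protocol schedules the review of systems at baseline and at every follow-up visit, so a baseline value is planned for each participant.

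The reason is given in two places. Protocol 5.3 says of chronic high-dose vitamin A: "The effects of toxicity may include hepatomegaly, elevated blood lipid levels, bone changes, and increased intracranial pressure". Protocol 4.4.3, on combined use with tetracyclines, says that "each drug has the potential to cause intracranial hypertension" and adds: "Specific questions regarding headaches and attention to optic nerve for presence of papilledema will be noted at each visit". SAP 14.6 applies the headache and papilledema assessments to all participants.

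For analysis, SAP 14.6 plans "Number and percentage of participants experiencing optic nerve papilledema in each eye, headache classified by severity", by cohort and overall, together with a by-participant listing whose fields are not named. The shell, Table 20 ("Summary of Optic Nerve Papilledema, Headache, and Medication Assessment"), has four headache rows (None, Mild, Moderate, Severe) under baseline and under follow-up visits. It has no frequency row and no shift or change column. Its footnote reads: "Denominators are the number of participants in the safety population with a non-missing value for the parameter at the specified visit".

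Elsewhere the SAP does compare with baseline. Section 13.2 and Table 14 give laboratory abnormalities as a shift from baseline, and section 14.5 gives change in intraocular pressure.

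**The concern.** The study is uncontrolled, so each participant's own baseline is the only comparator for a safety symptom. Table 20 does not use it in a paired way. It shows the spread of severity at baseline and again at follow-up, but not who moved. With about five people per cohort, one person worsening while another improves leaves the counts unchanged. Frequency is assessed but enters no planned summary.

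Pre-existing headache is possible: neither the participant exclusion list nor the study eye exclusion list mentions headache or migraine. At stake is whether the planned summary can show new or worsening headache at the individual level, particularly at the higher dose. No efficacy conclusion depends on this.

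**Working it through.** The documents give no figure on this point to reproduce. The check has two parts.

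**1. What is collected against what is tabulated**

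- Severity at each visit: collected; tabulated as counts per visit; not paired with baseline.
- Frequency at each visit: collected; not tabulated. Someone whose mild headaches become more frequent stays in the Mild row, so Table 20 cannot show the change, whatever the cohort size.
- Denominator: participants with a value at that visit, so follow-up counts need not describe the same people as baseline counts.

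**2. How much individual change identical counts can hide**

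Take n = 5, the number per cohort that SAP 5.1 aims to have in the primary outcome analysis. The baseline patterns are assumed, since the documents report none. For each, count the follow-up arrangements across the five people that reproduce the baseline counts exactly. The number is 5! divided by the product of the factorials of the category counts.

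- *5 None.* 5!/5! = 1 arrangement, with nobody worse. Any recorded new headache shows as at least 1 of 5.
- *4 None, 1 Mild.* 5!/(4!·1!) = 5 arrangements. In one, the same person has the headache. In the other 4, someone else has a new one.
- *3 None, 2 Mild.* 5!/(3!·2!) = 10 arrangements. In one, nobody changes. In 9, at least one person has a new headache. The number of people with a new headache ranges from 0 to min(2, 3) = 2, that is 0% to 40% of five.
- *3 None, 1 Mild, 1 Moderate.* 5!/(3!·1!·1!) = 20 arrangements. In one, nobody changes, and in 19 at least one person is worse. In 2 the headaches stay with the same two people, so 20 − 2 = 18 contain a new headache.

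These are counts of possible arrangements. They are not probabilities, and they do not predict what the study will show.

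*Missing values.* If nobody has headache at baseline (0 of 5) and the one person who develops it has no value at the next visit, Table 20 shows 0 of 4.

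New or worse headache is therefore hidden in Table 20 only when offset by improvement or lost to a missing value. A rise in frequency at constant severity is always hidden there.

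**The case against.** The strongest reply is that Table 20 is not the only place to look.

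- **Listing.** SAP 14.6 and the opening of section 14 promise listings, and protocol 9.1 describes the analysis as mainly descriptive and by participant. With so few people, a reader could probably trace severity by hand. This stands in part: the fields are not named, frequency is not guaranteed, and Listings 1 to 3 in the mock shells do not cover headache.
- **Adverse events.** Under Appendix 2, adverse events are assessed at the follow-up visits. SAP 12.1 lists them with severity and relatedness and tabulates them in Tables 12 and 13. A headache recorded as an adverse event is therefore counted. This also stands in part: the documents do not say when a headache noted in the review of systems becomes an adverse event.
- **Format.** Table 21 also gives categorical findings as per-visit counts without a shift, so Table 20 follows a house style. However, Table 14 handles laboratory abnormality, also categorical, as change from baseline, so a paired summary is already within the SAP's practice.
- **Sample size.** Table 20 uses the safety population, which may exceed five: SAP 5.1 allows eight participants in Cohort 1 and up to ten in Cohort 2. This is correct, and it makes the counts above illustrations only.
- **Forms.** The case report form is not shown, so it is unknown whether frequency is graded. This stands and limits what can be asked for on frequency.

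**Conclusion.** The point holds as a minor gap in a descriptive safety table. Headache severity is summarised without pairing, in a study whose only comparator is the participant's own baseline, and frequency is not summarised at all. The listing and the adverse event tables reduce the gap, but as written they are not certain to close it. The size depends on the headache pattern at baseline: nothing is hidden by offsetting if nobody has headache then, while 18 of 20 identical-count arrangements contain a new headache in the three None, one Mild, one Moderate illustration.

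Three stronger readings are not supported.

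- A reader might infer that new headaches in general would go unseen. They would not: the baseline block stands beside the follow-up blocks, so a net rise shows.
- A reader might infer that long-standing headache would be mistaken for harm. The same baseline block shows it was already there, and the shell's event header also covers the None and No rows.
- A reader might extend the point to papilledema. It is tabulated as yes or no per eye with a baseline row, and nothing in the documents suggests baseline cases that could offset new ones.

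The 0% to 40% range likewise illustrates one assumed pattern and does not estimate hidden harm.

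**What to change.** In SAP 14.6 and Table 20, add for each follow-up visit the number and percentage of participants whose headache severity is higher than at their own baseline. The denominator should be participants with a value at both visits. This is the same kind of shift that Table 14 already gives for laboratory results. Keep the existing per-visit counts.

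In the by-participant listing, name headache frequency and severity as fields, with baseline beside follow-up. Count increases in frequency only if the form records frequency in grades; otherwise list it. It would also help to state how a headache noted in the review of systems relates to adverse event recording, so that readers know what Tables 12 and 13 contain.

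The cost is SAP and shell wording plus a little programming, using data the protocol already plans to collect. A frequency count would also require a check of the form. No change to monitoring, dosing or stopping rules is implied.
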